#### **8.1.3 Adverse Events of Pigmentary Changes**

For any disease progression (DP) tumor responses due to LBD defined in Method 1 (i.e., based on only meeting the LBD criterion, not based on meeting either the tumor thickness criterion or subject receiving Standard of Care), if the subject has an AE of pigmentary changes in the eye being assessed **and** the Investigator response to eCRF question is "No" per section 8.1.2 on or after the start date of this AE, then the tumor response will be classified as stable disease (SD).

An AE of pigmentary changes is any AE where the Preferred Term (PT) is "Retinal depigmentation" or "Retinal pigment epitheliopathy".

Confidential

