#### 2. Based on maximum thickness and LBD, subject receiving Standard of Care, and Investigators determination of progression

Confidential

Tumor response (PR, SD, or DP) will be based on the algorithm defined method 1 above with the addition of the Investigator determination of progression criteria provided in Section 8.1.2.

3. Based on maximum thickness and LBD, subject receiving Standard of Care, Investigators determination of progression, and adverse events of pigmentary changes

Tumor response (PR, SD, or DP) will be based on the algorithm defined method 1 with the additional criteria of both Investigator determination (Section 8.1.2) and AE of pigmentary changes provided in (Section 8.1.3).

As this method accounts for the Investigator determination of progression per protocol sections 10.3.4 and 10.3.7, it will be considered the primary method for describing the results in the clinical study report.

For each of these 3 methods of determining tumor response, the tumor response results will be presented at each visit, as well as an overall summary table. The overall summary table will present the results at Month 12 using last observation carried forward (LOCF) as well as the subject's last visit, including follow-up. For the overall summary table, the table will provide which of the LBD and maximum thickness criteria were met for the response (or both) as well as a category for "Treated with standard of care prior to Progression" (i.e., this category will be for subjects who were treated with standard of care prior to reaching the progression criteria).

An additional summary of the Summary of Tumor Response Tables (3 tables for Methods 1-3) including just site 009 (i.e., the site excluded from the Efficacy Evaluable Population) will be performed.

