#### 8.1.1 Maximum Thickness and LBD Tumor Response Criteria

All tumors will be assessed for thickness by B-scan ultrasound and for largest basal diameter (LBD) by Fundus Photos.

Criteria to classify tumor response will be:

- **Partial Response (PR):**
  - Any reduction > 0.5 mm in the maximum thickness of the CM from baseline (B-scan) and no progression (ie, and increase <1.0 mm) based on LBD (Fundus Photos), **OR**
  - Any reduction > 0.5 mm in the LBD of the CM from baseline (Fundus Photos) and no progression (ie, and increase <0.5 mm) based on tumor thickness (B-scan)
- **Stable Disease (SD):**
  - Maximum thickness of the CM is within -0.5 mm to +0.5 mm (inclusive) change from baseline (B-scan), **AND**
  - Maximum LBD of the CM is within -0.5 mm to +1.0 mm (inclusive) change in diameter from baseline (Fundus Photos)
- **Disease Progression:**
  - Any increase > 0.5 mm in the maximum thickness of the CM from baseline not judged by the Investigator to be due to inflammation/swelling or hemorrhage (B-scan), **OR**
  - Any increase > 1.0 mm in the LBD of the CM from baseline not judged by the Investigator to be due to inflammation/swelling, hemorrhage or pigmentary changes (Fundus Photos)

Confidential

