#### **8.1.2 Investigator Determination of Progression**

The investigator determination of progression is based on the corresponding Investigator judgement of progression eCRF question:

*Did the subject meet the protocol defined disease progression criteria and not yet receive additional therapy with standard of care (plaque brachytherapy, proton beam radiotherapy or enucleation) or additional therapy with AU-011 since the previous visit? (Yes/No Response).*

If the Response to this eCRF question is "No" and the subject met the criteria for disease progression (DP) based on the maximum thickness and LBD criteria defined in Section 8.1.1, then the tumor response will be classified as Stable Disease (SD).

Note that if a subject has started standard of care, they will be considered as having met the disease progression (DP) criteria from the date standard of care was administered.

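### SAP 8.1.3 does not say which visit's Investigator 'No' counts, so the primary tumour-response method (Method 3) either equals Method 2 or can turn progression on basal diameter into stable disease using another visit's answer

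*SAP*

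**What the plan says.** SAP 8.1 defines three methods. Method 1 uses maximum thickness, LBD and receipt of standard of care, and leaves Investigator judgement out. Method 2 is "method 1 above with the addition of the Investigator determination of progression criteria provided in Section 8.1.2". Method 3 is Method 1 "with the additional criteria of both Investigator determination (Section 8.1.2) and AE of pigmentary changes provided in (Section 8.1.3"). Of Method 3 the SAP says "it will be considered the primary method for describing the results in the clinical study report", because it takes account of the Investigator's determination under protocol 10.3.4 and 10.3.7.

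The rules that these methods use are:

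- **8.1.1.** DP is a thickness increase above 0.5 mm or an LBD increase above 1.0 mm, unless the Investigator puts it down to inflammation or bleeding or, for LBD only, to pigment. Either is enough.
- **8.1.2.** When measured DP meets an Investigator 'No', "then the tumor response will be classified as Stable Disease (SD"). No AE is required. A missing answer is filled from the subject's next non-missing one; if there is none, the measurements alone decide.
- **8.1.3.** This covers Method 1 DP "based on only meeting the LBD criterion, not based on meeting either the tumor thickness criterion or subject receiving Standard of Care". If the eye has a pigmentary AE and the Investigator's answer is 'No' "on or after the start date of this AE, then the tumor response will be classified as stable disease (SD").

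The eCRF question has two parts. It asks whether the protocol's progression criteria were met and whether the subject had not yet had standard of care or additional AU-011 since the previous visit. Results are shown at each visit and, in an overall table, at Month 12 LOCF and Last Visit.

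**The concern.** Section 8.1.3 is the only thing that separates the primary method from Method 2. It needs a 'No', as 8.1.2 does, but dates that 'No' from the start of the AE and not from the visit being classified. Two programmers could read it differently and produce different primary tables.

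If an answer from another visit may be used, the primary method can set aside an Investigator's statement that the protocol criteria were met. Protocol 10.3.4 already excludes LBD increases that the Investigator attributes to pigmentary changes. A 'Yes' therefore already means that pigment was not judged to be the cause. Nor need a later 'No' be a change of mind. Protocol 8.3.3 allows AU-011 retreatment after progression, and in the SAP only standard of care forces DP. A confirmed progressor who is then retreated with AU-011 can be answered 'No' at the next visit because of the second part of the question.

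**Working it through.** The plan gives no figure to reproduce, so the check is one of logic.

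**Step 1: overlap.** 8.1.1 joins thickness and LBD with OR, so LBD-only DP falls within 8.1.2. That section turns it into SD on a 'No', with or without an AE. Method 3 applies 8.1.2 and 8.1.3 together, so 8.1.3 matters only where 8.1.2 has left the visit as DP. That happens where the visit's answer, after the missing-answer rule, is 'Yes', or where there is no answer at or after the visit.

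**Step 2: cases.** LBD-only DP, pigmentary AE present, no standard of care:

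| Answer for the classified visit | 'No' at another visit on or after AE start | Method 2 | Method 3, same-visit reading | Method 3, any-visit reading |
|---|---|---|---|---|
| No | irrelevant | SD | SD | SD |
| Yes | none | DP | DP | DP |
| Yes | present | DP | DP | **SD** |
| None at or after the visit | none | DP | DP | DP |
| None at or after the visit | earlier 'No' | DP | DP | **SD** |

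**Step 3: full enumeration over three visits.** Inputs:

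- DP source at each visit (none, LBD only, thickness): 3³ = 27 patterns
- answer at each visit (Yes, No, missing): 3³ = 27 patterns
- standard-of-care start (none or visit 1 to 3): 4
- AE start (none or visit 1 to 3): 4
- visit classified: 3

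The total is 27 × 27 × 4 × 4 × 3 = 34,992 states. These are logical combinations and not expected patient frequencies.

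| Reading of the 'No' in 8.1.3 | States where Method 3 differs from Method 2 | Direction | Visit's answer after the 8.1.2 fill |
|---|---|---|---|
| The classified visit's answer | 0 | none | not applicable |
| At the classified visit or later, on or after AE start | 594 | all DP to SD | Yes in all 594 (513 recorded at the visit, 81 filled from a later one) |
| At any visit on or after AE start | 810 | all DP to SD | Yes in 720 (621 recorded + 99 filled); none in 90 |

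Under each cross-visit reading, the DP visit comes before the AE start in 324 of the differing states. Section 8.1.3 does not rule this out.

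**Step 4: per-subject size.** One reclassified subject adds 1/n to the control rate. At Cohort 12's maximum of 15, 1/15 = 6.7 percentage points. At the approximately 60 planned, 1/60 = 1.7 points.

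**The case against.** **The harmful reading may not be the intended one.** Section 8.1.3 refers back to 8.1.2, which works visit by visit, and responses are reported by visit. The AE-date phrase can be read as limiting which visits qualify, not as permission to borrow an answer. On that reading no result is biased. This stands, and it makes the bias conditional. It does not rescue Method 3, which then duplicates Method 2.

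**The reach is limited.** If only the classified visit or a later one can supply the 'No', Last Visit normally has nothing later to borrow, so the methods would normally agree there. This stands for that endpoint under that reading. It does not cover Month 12 or the individual visits. For the two carried-forward endpoints, the SAP imputes thickness and LBD but does not say which visit's Investigator answer goes with them.

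**The damage is visible and the study is exploratory.** All three methods are tabulated, nothing is tested, and the primary objective is safety. This is partly right: a net difference between Methods 2 and 3 would show in the tables. The subjects behind it would not be identified, and Method 3 is still the one chosen to describe the results.

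**Method 3 has its own rationale.** It names pigmentary change, which protocol 10.3.4 recognises. But a 'No' under Method 2 can already reflect pigment, and the stated reason, accounting for the Investigator's determination, fits Method 2 equally.

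**The intent may have been stricter.** If LBD-only DP was meant to need both the AE and the 'No' before becoming SD, Method 3 would be harder than Method 2: 1,566 of the 34,992 states would move from SD to DP. The text does not say this, because it applies 8.1.2 as well and 8.1.2 has no AE condition.

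**Conclusion.** The rule is defective on either reading. With a same-visit 'No', 8.1.3 is redundant and the primary method is Method 2 under another name. With a 'No' from another visit, every difference from Method 2 runs from DP to SD.

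A reader might infer three stronger things that the documents do not support:

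- **That Method 3 is biased as it stands.** The bias exists only under the cross-visit reading, which the wording allows but does not require.
- **That 8.1.3 can act only by overriding a 'Yes'.** Under the widest reading it can also act where no answer exists at or after the visit, by using an earlier 'No'. No confirmed progression is overturned there.
- **That the effect on the control rate is known.** The documents do not say how many subjects have LBD-only DP, a qualifying AE and mixed answers. The 6.7 points is the effect of one subject in a group of 15 and is not an estimate.

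The conclusion rests on the SAP as written: 8.1.2 and 8.1.3 both apply in Method 3, and DP is met by thickness or LBD.

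**What to change.** 1. In 8.1.3, require that the 'No' be the answer for the visit being classified, after the 8.1.2 missing-answer rule, and that this visit fall on or after the AE start date.
2. State which visit's Investigator answer applies at Month 12 LOCF and at Last Visit.
3. Acknowledge that Methods 2 and 3 then coincide, and name Method 2 as primary.
4. Add a listing of subjects whose class differs between Methods 1, 2 and 3.

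If the sponsor instead meant LBD-only DP to become SD only with both the AE and the 'No', the SAP must say that 8.1.2 does not apply to those cases in Method 3. It should also acknowledge that Method 3 is then stricter than Method 2.

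The cost is SAP wording and one listing. The reported control rate may be lower; the documents do not allow the amount to be stated.

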#### 8.1.4 Subjects Receiving Standard of Care

The date of the subject receiving standard of care will be from the Prior and Concomitant Procedure/Surgery eCRF page. Standard of Care includes the eye procedures categorized as: 'Radiotherapy to eye', 'Brachytherapy to eye' or 'Photodynamic therapy' (i.e., dictionary derived terms).

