8.3.3. Additional Therapy

Additional therapy with AU-011 at the maximum tolerated and feasible dose of 3 repeat doses of 80 µg each followed by two laser applications (treatment regimen) can be provided to:

- ensure that all subjects are able to receive the maximum tolerated and feasible dose, particularly for subjects that were treated with lower doses previously
- allow additional treatment regimens in subjects that have stable disease (treatment extension)
- allow retreatment in subjects that meet the protocol definition of disease progression

If the fovea is near the tumor edge, an adjustment to the laser procedure should be performed on each treatment day as outlined in section 8.2.2 and the Injection and Laser Procedure Manual. Subjects may be considered for additional therapy with AU-011 (defined above) after Visit 11 (Week 12) and only after inflammation from the previous treatment has resolved or when the inflammation is minimal and decreasing based on investigator judgement. Additional therapy with AU-011 must be approved by the Sponsor on a case-by-case basis prior to the initiation of therapy. Alternatively, also after Visit 11 (Week 12 Visit), standard of care therapy, including plaque brachytherapy, proton beam radiotherapy or enucleation may be used if the subject meets the protocol definition of disease progression or the Investigator judges that the disease is progressing per their clinical judgement for increases in tumor thickness or LBD that are less than the protocol definition of disease progression. Before additional therapy is performed, the following protocol assessments must be collected in the study eye unless otherwise noted: ETDRS BCVA (both eyes), slit lamp biomicroscopy, IOP measurement, fundoscopy, Fundus photos, EDI-OCT, B-scan ultrasound, A-scan ultrasound, OCTA (Cohorts 6 to 9 only) and a visual field examination. If these assessments have not been performed at the most recent study visit, an unscheduled visit is required to be performed to obtain these assessments.

The criteria for implementing additional therapy due to disease progression is as follows:

• An increase on B-scan ultrasound of >0.5 mm in melanoma thickness from baseline, not due to intralesional hemorrhage/inflammation

OR

• An increase on digital fundus photos of >1.0 mm in melanoma diameter from baseline, not due to intralesional hemorrhage/inflammation or pigmentary changes

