#### 1. Based on maximum thickness and LBD and subject receiving Standard of Care

Tumor response (PR, SD, or DP) will be based on the algorithm as defined in Section 8.1.1, with the modification that Investigator determination mentioned in DP definition will not be considered and if a subject receives standard of care they will be considered as having met the disease progression (DP) criteria from the date standard of care was administered.

Note that for the Month 12 LOCF and Last Visit timepoints:

- If a patient receives standard of care prior to their Month 12 Visit, the subject will be considered as having met DP, even if the LBD and/or tumor thickness assessments are being LOCF'd from a time-point previous to the SOC being administered.
- Similarly, if a patient receives standard of care prior to their Last Visit, the subject will be considered as having met DP, even if the LBD and/or tumor thickness assessments are being LOCF'd from a time-point previous to the SOC being administered.

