### **Missing LBD or maximum thickness values:**

If both the LBD and maximum thickness values at a visit are missing, the tumor response will be set to missing for that visit.

If 1 of the 2 measurements is missing, the tumor response will be determined by just considering criteria as applied to the non-missing measurement. (note: this rule does not apply to the Month 12 LOCF and Last Visit endpoints where an LOCF algorithm for both tumor thickness and LBD will be applied, as described below).

Additionally, the following LOCF algorithm for tumor thickness and LBD will be applied for tumor response relative the Month 12 LOCF and Last Visit endpoints only (i.e., this LOCF algorithm does not apply to the individual visits, only the Month 12 LOCF and Last Visit timepoints).

- If a subject is missing a tumor thickness and/or their LBD assessments as a scheduled visit, an LOCF approach will be used to impute the missing data from the previous visits (ie, an LOCF approach will be applied to the tumor thickness and separately an LOCF approach will be applied to the LBD). If a patient has no non-missing post-baseline visits, the baseline value will be used. The assessment of tumor response (i.e., as described above) will be applied using the LOCF'd tumor thickness and LBD values.

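### SAP 8.1.4 leaves enucleation out of the coded standard-of-care list, so removal of the study eye does not itself trigger progression and can be scored as stable disease at Month 12 LOCF and Last Visit

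*SAP*

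**What the plan says.** **The rule.** SAP 8.1, Method 1, states that "if a subject receives standard of care they will be considered as having met the disease progression (DP) criteria", with effect from the date of the procedure. Methods 2 and 3 build on Method 1, and Method 3 is the primary method for the study report. For Month 12 LOCF and Last Visit, SAP 8.1 adds that standard of care given before the time point means DP even when the sizes are carried forward from before the procedure.

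**What counts as standard of care.** SAP 8.1.4 gives the source, "The date of the subject receiving standard of care will be from the Prior and Concomitant Procedure/Surgery eCRF page", and then the list: "Standard of Care includes the eye procedures categorized as: 'Radiotherapy to eye', 'Brachytherapy to eye' or 'Photodynamic therapy". It describes these as terms derived from the coding dictionary.

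**The same concept elsewhere.**
- Protocol 8.3.3: "standard of care therapy, including plaque brachytherapy, proton beam radiotherapy or enucleation may be used". It allows this at protocol-defined progression, and also on Investigator judgement "for increases in tumor thickness or LBD that are less than the protocol definition of disease progression".
- SAP 8.1.2, in the eCRF question on progression: "additional therapy with standard of care (plaque brachytherapy, proton beam radiotherapy or enucleation".
- Protocol 4.2 describes photodynamic therapy as an explored alternative that is not standard of care.

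**Missing sizes.** For individual visits, SAP 8.1.1 says: "If both the LBD and maximum thickness values at a visit are missing, the tumor response will be set to missing for that visit". For Month 12 LOCF and Last Visit, thickness and largest basal diameter (LBD) are each carried forward and then classified: "The assessment of tumor response (i.e., as described above) will be applied using the LOCF'd tumor thickness and LBD values".

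**The concern.** The SAP clearly means standard of care to override carried-forward sizes. That override works only for procedures that the 8.1.4 list picks up. The list omits one of the three treatments that the protocol and the eCRF question call standard of care.

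Enucleation is also the case where the override is most needed, because no tumour can be measured afterwards. The two LOCF endpoints must then rest on values from before the operation. Standard of care is allowed for growth below the protocol limits, so those values can qualify as stable disease.

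Two subjects with the same local course would then be scored in opposite ways: DP after a plaque, tumour control after eye removal. The enucleated subject would also be left out of the overall summary table's category for subjects given standard of care before reaching progression. For a subject below the limits at the last measurement, the error can only make tumour control look better.

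**Working it through.** The plan gives no figure to reproduce: the study is descriptive, with no sample size calculation. The check is to run one subject through the SAP's rules.

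**Inputs**
- Progression limits (SAP 8.1.1): thickness increase above 0.5 mm, or LBD increase above 1.0 mm.
- Standard of care before the time point gives DP (SAP 8.1, Method 1, carried into Methods 2 and 3).
- Methods 2 and 3: an Investigator answer of 'No' turns measured DP into stable disease (SD) (SAP 8.1.2).
- Tumour control is PR plus SD (SAP 8.1.7).
- Planned numbers: about 60 overall, up to 15 in Cohort 12, about 6 in each of Cohorts 10 and 11, and 3 in an unexpanded escalation cohort.
- The size changes below are illustrative assumptions.

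**Step 1. Month 12 LOCF and Last Visit.** The subject has the procedure before the time point, has had no earlier radiotherapy, and has no AE of pigmentary changes.

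| Last sizes before procedure | Investigator answer | Enucleation, 8.1.4 as written (Methods 1 / 2 / 3) | Enucleation added to list | Brachytherapy, 8.1.4 as written |
|---|---|---|---|---|
| Thickness +0.4 mm, LBD +0.8 mm | Yes, No or missing | SD / SD / SD | DP / DP / DP | DP / DP / DP |
| Thickness +0.7 mm, LBD +0.8 mm | Yes or missing | DP / DP / DP | DP / DP / DP | DP / DP / DP |
| Thickness +0.7 mm, LBD +0.8 mm | No | DP / SD / SD | DP / DP / DP | DP / DP / DP |

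The third row can plausibly arise. The eCRF question asks whether progression criteria were met and, in the same sentence, whether standard of care had not yet been given, with enucleation named. After eye removal the literal answer is 'No'. SAP 8.1.2 also fills a missing answer with the next non-missing one, so a later 'No' can reach back. The safeguard in 8.1.2, that starting standard of care means DP, is put into effect through the 8.1.4 list.

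**Step 2. Individual visits after enucleation.** Both sizes are missing, so the response is missing. Under SAP 4.8 missing subjects generally leave the percentage. This is a loss from the denominator, not a score of tumour control.

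**Step 3. Size per misclassified subject,** 100/n percentage points:
- 100/60 = 1.7
- 100/15 = 6.7
- 100/6 = 16.7
- 100/3 = 33.3

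No probability is attached to the event. The only enucleation rate in the documents, 4% in Protocol 4.2, is for eyes already irradiated. Such a subject in this trial would be DP from the radiation date.

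**The case against.** **The list may not be closed.** SAP 8.1.4 uses a verb of inclusion, and 8.1.2 names enucleation and says in the same section that starting standard of care means DP. On that reading this is an inconsistency between neighbouring sections, not a decision to exclude. That is fair as to intent. But 8.1.4 is the section that fixes the coded terms and the date, and a program written from it would miss enucleation.

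**The affected group is narrow.** Protocol 4.1 says enucleation is reserved for the most symptomatic and recurrent disease. Misclassification needs enucleation without earlier radiotherapy, plus either last sizes below the limits or a 'No' under Methods 2 and 3. This stands. The list may also reflect only the procedures found in the data, since SAP v5.0 followed the first database lock, but the SAP does not say so.

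**The event is not hidden, and efficacy is secondary.** The primary objective is safety and no hypothesis is tested. An enucleation would still appear among concomitant procedures (Table 14.1.4.4), in the additional-therapy counts (SAP 9.6.7) and in Listing 16.3.11. This stands and limits the consequence, but it does not correct the response tables. Including photodynamic therapy can only add DP, so that part of the list is conservative.

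**Visual acuity.** A reader might infer that the omission also lets an enucleated subject count as vision-preserved. The documents do not support that as a consequence of 8.1.4. For recognised standard of care before Week 39, SAP 8.2 also uses the two most recent visits before the procedure. With later acuity missing, a plaque subject and an enucleated subject are scored alike. If removal falls between Weeks 39 and 52, a qualifying loss at Week 39 with no later data is a failure on either reading, and no qualifying loss is not a failure on either. Counting failure from the date of enucleation would be a new endpoint rule, contrary to the SAP's stated censoring after standard of care.

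**Conclusion.** SAP 8.1.4 is wrong as written: it contradicts Protocol 8.3.3 and SAP 8.1.2, and SAP 4.9 does not mention the difference among its changes to the response criteria. The effect is limited to tumour response. At Month 12 LOCF and Last Visit an enucleated subject can be scored as stable disease; at individual visits the response goes missing.

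A reader might go further and infer that every enucleated subject escapes progression. That is not so. A subject already over a limit is DP under Method 1, and under Methods 2 and 3 unless the Investigator's answer is 'No'. A subject irradiated before enucleation is already DP.

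The shift of 1.7, 6.7, 16.7 or 33.3 points per subject is conditional on such a case. It assumes the planned cohort sizes and a program that follows 8.1.4 literally. No enucleation is documented, so the actual effect may be nil.

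**What to change.** 1. In SAP 8.1.4, add the dictionary-derived term(s) for enucleation of the study eye, so that DP applies from that date in Methods 1 to 3. State that this takes precedence over the rule that sets the response to missing when both sizes are missing. The existing notes in SAP 8.1 on Month 12 LOCF and Last Visit then cover carried-forward values without further change.
2. Reconcile the list with Protocol 8.3.3 and SAP 8.1.2, and state why photodynamic therapy is or is not included, given Protocol 4.2.
3. Record the change in SAP 4.9.

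No change to the acuity rules in SAP 8.2 is needed on this account.

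The cost is a few lines of text and one or more coded terms in one derivation. The procedure page already supplies the date, so no new data are needed. If no study eye was enucleated, no result changes and the contradiction is removed. If one was, tumour control falls by 1/n wherever that subject had been scored as controlled.
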